5.3 Exclusion criteria

Patients eligible for this study must not meet **any** of the following criteria at screening:

1. Patients with prior treatment with ruxolitinib or other JAK inhibitors.
2. Patients with known hypersensitivity to ruxolitinib or any of its excipients.
3. Patients with inadequate liver function defined by any of these:
Total bilirubin $\geq 2.5 \times \text{ULN}$ and subsequent determination of direct bilirubin $\geq 2.5 \times \text{ULN}$;
Alanine aminotransferase (ALT) $> 2.5 \times \text{ULN}$; Aspartate aminotransferase (AST) $> 2.5 \times \text{ULN}$.
4. Patients with severely impaired renal function defined by:
Serum creatinine $> 2 \text{ mg/dL}$.
5. Patients with active bacterial, fungal, parasitic, or viral infection which requires therapy.
6. Impairment of gastrointestinal (GI) function or GI disease that may significantly alter the absorption of ruxolitinib (e.g., ulcerative diseases, uncontrolled nausea, vomiting, diarrhea, malabsorption syndrome, small bowel resection).
7. Known history of human immunodeficiency virus (HIV) infection or other immunodeficiency syndromes such as X-linked agammaglobulinemia and common variable immune deficiency.
8. Active hepatitis A, B or C infection, which requires treatment.
9. History of progressive multifocal leuko-encephalopathy (PML).
10. History or current diagnosis of uncontrolled or significant cardiac disease, including any of the following:
 - Myocardial infarction within last 6 months
 - Uncontrolled congestive heart failure
 - Unstable angina within last 6 months
 - Clinically significant (symptomatic) cardiac arrhythmias (e.g., sustained ventricular tachycardia, and clinically significant second or third degree AV block without a pacemaker)

11. Significant concurrent, uncontrolled medical condition, which in the investigator's opinion would jeopardize the safety of the patient or compliance with the protocol.
12. Patients being treated concurrently with a strong (potent) systemic inhibitor or inducer of CYP3A4 ([Appendix 1](#)) at the time of Screening.
13. Patients under ongoing treatment with another investigational medication or having been treated with an investigational medication within 30 days or 5 half-lives (whichever is longer) prior to the first dose of study treatment.
14. Patients with a history of malignancy in the past 3 years, except for well-controlled early stage squamous or basal cell carcinoma in situ.
15. Patients eligible for stem cell transplantation.
16. Pregnant or nursing (lactating) women.
17. Women of child-bearing potential, defined as all women physiologically capable of becoming pregnant, unless they are using highly effective methods of contraception throughout the study duration inclusive of 30 day safety follow up. Highly effective contraception methods include:
 - Total abstinence (when this is in line with the preferred and usual lifestyle of the subject. Periodic abstinence (e.g., calendar, ovulation, symptothermal, post-ovulation methods) and withdrawal are not acceptable methods of contraception
 - Female sterilization (have had surgical bilateral oophorectomy with or without hysterectomy), total hysterectomy or tubal ligation at least six weeks before screening. In case of oophorectomy alone, only when the reproductive status of the woman has been confirmed by follow up hormone level assessment
 - Male sterilization (at least 6 months prior to screening). The vasectomized male partner should be the sole partner for that subject.
 - Use of oral, injected or implanted hormonal methods of contraception or placement of an intrauterine device (IUD) or intrauterine system (IUS) or other forms of hormonal contraception that have comparable efficacy (failure rate <1%), for example hormone vaginal ring or transdermal hormone contraception. In case of use of oral contraception women should have been stable on the same pill for a minimum of 3 months before screening.

Women are considered post-menopausal and not of child bearing potential if they have had 12 months of natural (spontaneous) amenorrhea with an appropriate clinical profile (e.g. age appropriate, history of vasomotor symptoms) or have had surgical bilateral oophorectomy (with or without hysterectomy), total hysterectomy or tubal ligation at least six weeks ago. In the case of oophorectomy alone, only when the reproductive status of the woman has been confirmed by follow up hormone level assessment is she considered not of child bearing potential.

18. Subjects who are unable to comprehend or are unwilling to sign an informed consent form (ICF).

6 Treatment

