1.1 Overview of disease pathogenesis, epidemiology and current treatment

Myelofibrosis (MF) is a clonal hematologic neoplastic disease characterized by the presence of megakaryocyte proliferation and atypia, usually accompanied by either reticulin and/or collagen fibrosis (Tefferi 2008), splenomegaly, anemia, and debilitating constitutional symptoms that include fatigue, weight loss, pruritus, night sweats, fever, and bone, muscle, or abdominal pain (Mesa et al 2007, Abdel-Wahab, Levine 2009). MF can either be primary in origin (primary myelofibrosis, or PMF) or result from progression of polycythemia vera or essential thrombocythemia vera (Tefferi 2008). The median age at diagnosis of MF is approximately 65 years. Patients with myelofibrosis have shortened survival that ranges from a median of approximately 2 years to 11 years depending on the presence of certain risk factors that define their risk category including age, anemia, leukocytosis, etc.

Several prognostic risk scores that are based on survival outcomes have been developed in MF to better define treatment choices for physicians and therefore improve patient management. The International Prognostic Scoring System (IPSS) was developed by the International Working Group for Myeloproliferative Neoplasms Research and Treatment (IWG-MRT) (Cervantes et al 2009). The IPSS is used at diagnosis and employs five hematologic and clinical variables (age, leukocytosis, anemia, peripheral blood blasts and constitutional symptoms) to stratify patients in a low, intermediate-1, intermediate-2 and high-risk category. The dynamic IPSS (DIPSS) was subsequently developed to be used for patients evaluated after MF diagnosis (Gangat et al 2011). The DIPSS relies upon the same five variables as IPSS but utilizes the predictive value of selected cytogenetic abnormalities. These scoring systems are expected to facilitate categorizing patients to different risk groups, and thus assist physicians in recommending optimal treatment management plans.

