1.2.1.2.1 Clinical Pharmacology

Fifteen Phase I, nine Phase II and three Phase III clinical studies (two in MF, one in PV) provided clinical pharmacology data on ruxolitinib in healthy volunteers and in patients with MF, ET, PV, as well as in subjects with renal or hepatic impairment, prostate cancer, pancreatic cancer, MM or RA. Oral absorption of ruxolitinib is rapid and nearly complete, with $\geq 95\%$ absorption indicating high *in vivo* permeability in the human gastrointestinal tract, consistent with a Biopharmaceutical Classification System (BCS) Class I compound. Mean peak plasma concentrations (C_{max}) is achieved 1-2 h post-dose.

The effect of food on ruxolitinib exposure is minimal and is not expected to be clinically significant; as a result, the drug may be administered either with or without food. Dose proportional exposure is observed between 5 and 200 mg dose range with linear pharmacokinetics (PK).

Plasma protein binding is approximately 97% *in vitro*. There is moderate distribution to organs and tissues with no long-term retention of drug-related material in preclinical species and limited drug penetration into the central nervous system (CNS) or across the blood-brain barrier. There is $>95\%$ [^{14}C] drug recovery in a mass balance study with 74% and 22% of the dose excreted in urine and feces of healthy subjects, respectively. Less than 1% of the administered dose is recovered in urine and feces as unchanged parent drug. The mean terminal elimination half-life ($t_{1/2}$) is ~ 3 h with no appreciable accumulation of either parent or metabolites with twice daily dosing. Metabolism is predominantly via the cytochrome P450 isozyme CYP3A4 to yield oxygenated and subsequent conjugated metabolites. Oxidative metabolites of ruxolitinib retain pharmacological activity albeit with one half to one fifth of the activity of the parent compound. *Ex vivo* pharmacokinetic/pharmacodynamic analysis indicates that the total of 8 active metabolites contribute to 18% of the overall pharmacodynamics activity of ruxolitinib. When administering ruxolitinib with strong CYP3A4 inhibitors, the total daily dose should be reduced by approximately 50%. No dose adjustment is necessary when co-administering ruxolitinib with strong CYP3A4 inducers. No

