dose adjustment is necessary when co-administering ruxolitinib with CYP3A4 substrates. Ruxolitinib did not decrease the exposure of a fixed dose oral contraceptive metabolized via the CYP3A4 pathway, thus demonstrating lack of CYP3A4 induction potential.

In patients with severe renal impairment [creatinine clearance (Cl_{cr}) < 30 mL/min], the recommended starting dose based on platelet count should be reduced by approximately 50% to be administered twice a day. Patients on hemodialysis should initiate ruxolitinib with a single dose of 15 mg or 20 mg (or two doses of 10 mg given 12 hour apart) based on platelet counts on day of hemodialysis with subsequent doses only on hemodialysis days and following each hemodialysis session. Ruxolitinib doses should be titrated based on individual safety and efficacy.

In patients with mild, moderate or severe hepatic impairment, the recommended starting dose based on platelet count should be reduced by approximately 50% with subsequent dose titration based on individual safety and efficacy.

Ruxolitinib PK in healthy volunteers was largely comparable between Japanese, Chinese and Western subjects and did not lead to a conclusion of meaningful ethnic differences.

[figure not shown]
Baseline elevations in inflammatory markers such as tumor necrosis factor alpha (TNF α), interleukin (IL)-6, and C-reactive protein (CRP) noted in patients with MF were associated with constitutional symptoms such as fatigue, pruritus, and night sweats. Decreases were observed in these markers over the 24 weeks of treatment with ruxolitinib, with no evidence that patients became refractory to the effects of ruxolitinib treatment.

Please refer to the [Investigator Brochure] for additional details on pharmacokinetics and pharmacodynamics.

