6.1.1 Dosing regimen

Table 6-2 Dose and treatment schedule

Treatment Period 1 (INC424/Placebo - Blinded)

Study treatments	Pharmaceutical form and route of administration	Dose	Frequency and/or Regimen
INC424/ Placebo	Tablet for oral use	10 mg BID (2 tablets of INC424 5mg/placebo BID)	Daily

Study treatment will be administered orally twice per day at a dose of 10 mg BID, given as 2 tablets of INC424 5mg / placebo ([Table 6-2](#)). Study treatment should be taken orally twice daily, approximately 12 hours apart (morning and night) without regards to food. Study treatment will be self-administered by the patient in an outpatient setting, and each investigator should instruct the patient to take the study drug as per protocol. All dosages taken by the patient must be recorded on the Dosage Administration Record case report form (CRF).

Patients should be instructed not to take study treatment at Week 12, Week 24 and Week 48 visit (and every 12 weeks thereafter) on the day of the scheduled pre-dose blood collection ([Section 7](#)). Dosing will be administered post blood collection at these visits.

Treatment Period 2 (INC424)

Once the patient progresses in Treatment Period 1 by splenomegaly or symptoms, the patient will start treatment with INC424 (ruxolitinib) 5/15/20 mg BID based on platelet count as per approved label ([Table 6-1](#) and [Table 6-3](#)).

Table 6-3 Dose and treatment schedule

Treatment Period 2 (INC424)

Study treatments	Pharmaceutical form and route of administration	Dose	Frequency and/or Regimen
INC424	Tablet for oral use	5/15/20 mg BID	Daily

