6.3 Dose modifications

6.3.1 Dose modification and dose delay

6.3.1.1 Dose modification for hematologic toxicity

Treatment Period 1

Dose reductions or interruptions for hematological changes are permitted in order to allow the patient to continue on the study treatment. The maximum allowed doses for different ranges of cytopenia is described in [Table 6-4](#). The objective of the dose adjustment rules is to optimize treatment response for each individual patient while avoiding significant cytopenia. Dosing may be restarted or increased following recovery of the hematologic parameter(s) to acceptable levels. Any patient requiring dose interruption continuously for more than 4 weeks

due to decreases in ANC or platelet (PLT) counts must be permanently discontinued from treatment. Hb levels decreasing below 8g/dL with an absolute drop of 3g/dL from baseline, will constitute a marker of progressive MF disease, if Hb levels fail to recover \geq 8g/dL following treatment interruption for two consecutive weeks. Such patients must permanently discontinue study treatment.

Table 6-4 Dose reductions and interruptions due to hematological changes – Treatment Period 1

Current Hb (g/dL)	Maximum allowable dose
< 8	Interrupt dosing (HOLD)
8 to < 10	Reduce total daily dose to 5 mg BID
Current PLT ($\times 10^9/L$)	
< 50	Interrupt dosing (HOLD)
50 to < 75	Reduce total daily dose to 5 mg BID
Current ANC ($\times 10^9/L$)	
< 0.5	Interrupt dosing (HOLD)
0.5 to < 0.75	Reduce total daily dose to 5 mg BID

All dose changes must be recorded on the Dosage Administration Record CRF.

Patients whose dose has been interrupted for more than 4 weeks for any reason are recommended to be permanently discontinued from study treatment.

Treatment Period 2

Dose reductions and interruptions for ruxolitinib treatment during ‘Treatment Period 2’ can be performed in accordance with the local label requirements. In countries where ruxolitinib is not currently approved, treatment should be discontinued for platelet counts less than $50 \times 10^9/L$ or absolute neutrophil counts less than $0.5 \times 10^9/L$. After recovery of blood counts above these levels, dosing may be re-started at 5 mg twice daily and gradually increased based on careful monitoring of complete blood cell count, including a white blood cell count differential.

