6.4.2 Permitted concomitant therapy requiring caution and/or action

The following medications have restrictions on use, dose, or require changes to the way in which study treatment is administered during the study:

- Systemic corticosteroid doses greater than the equivalent of 10 mg prednisolone per day are prohibited at any time during the study until treatment discontinuation.
- Inducers or inhibitors of the metabolizing enzyme CYP3A4 ([Appendix 1](#)):
 - When concomitant administration of a strong (potent) systemic inhibitor of CYP3A4 metabolizing enzymes or dual CYP2C9/CYP3A4 inhibitors (see [Appendix 1](#)) is required for patient management, the dose of study treatment must be reduced by approximately 50% to be administered twice daily by decreasing the twice daily dose or by decreasing the frequency of dosing to the corresponding once daily dose when twice daily dosing is not practical.
Note: No dose adjustment of study treatment is needed for use with topical ketoconazole.
Note: More frequent monitoring of hematology parameters and clinical signs and symptoms of ruxolitinib related adverse reactions is recommended upon initiation of a strong (potent) CYP3A4 inhibitor.
- No dose adjustment will be made when moderate CYP3A4 inducers (See [Appendix 1](#)) are co-administered with study treatment.
- Granulocyte growth factors are not allowed while study treatment is being administered but may be used for severe neutropenia at the Investigator's discretion while study medication is being withheld.

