7.1.2.1 Eligibility screening

Patients must meet all inclusion and exclusion criteria at screening in order to be eligible to proceed to the Treatment Period of the study.

Investigative staff will capture patient eligibility within source documents maintained at the site. Additionally the sites will enter patient information into the eCRF. Eligibility information in source documents will be made available during planned interim monitoring visits and compared against the clinical database for accuracy. The site will also be asked to confirm eligibility with the IRT system. Following registering in IRT for screening, patient eligibility data will be verified once all screening procedures are completed. The eligibility check will be embedded in the IRT system. Please refer and comply with detailed guidelines in the IRT manual. Only when eligibility data has been confirmed with the IRT system will the IRT assign study treatment.

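### Exclusion 4 judges severe renal impairment by serum creatinine alone, so some older or lighter patients with clearance below 30 mL/min can enter and start at 10 mg BID

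*Protocol*

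**What the plan says.** Protocol section 5.3, criterion 4, excludes "Patients with severely impaired renal function defined by" serum creatinine above 2 mg/dL. A value of 2.0 or less passes, and no other criterion names renal function. Section 5.2 sets no upper age limit and no weight limit.

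Section 1.2.1.2.1 defines severe renal impairment differently, as creatinine clearance below 30 mL/min, and says that for these patients "the recommended starting dose based on platelet count should be reduced by approximately 50% to be administered twice a day".

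For Treatment Period 1, section 6.1.1 states: "Study treatment will be administered orally twice per day at a dose of 10 mg BID". Section 6.3 has rules for blood counts, liver tests and other toxicity, but none for renal function at the start of treatment.

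Section 1.2.1.2.1 also advises halving the daily dose with strong CYP3A4 inhibitors. Section 6.4.2 turns that advice into an instruction: "the dose of study treatment must be reduced by approximately 50% to be administered twice daily". The renal advice has no such counterpart.

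**The concern.** Serum creatinine takes no account of age, weight or sex, all of which affect clearance. A creatinine cut-off of 2 mg/dL can therefore admit people whom the protocol's own pharmacology section would call severely impaired. The population makes this relevant: "The median age at diagnosis of MF is approximately 65 years", so many eligible patients will be older than that.

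A patient admitted this way and randomised to ruxolitinib may start above the dose that the protocol describes as recommended. Section 1.2.1.2.3 states that anaemia, thrombocytopenia and neutropenia are dose related. The main protocol response is Table 6-4, which acts only once a cytopenia has appeared. In Table 7-1 the first scheduled blood count after Day 1 is at Week 4.

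The matter is one of patient safety and internal consistency in Treatment Period 1. Treatment Period 2 is left out because section 6.1.1 ties its dosing to the approved label.

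**Working it through.** The plan gives no figure to reproduce here. The check is whether the two definitions select the same patients and, where they do not, how far the starting dose departs from the recommendation.

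**Inputs from the Protocol.** Creatinine cut-off 2 mg/dL (5.3); clearance cut-off 30 mL/min and a reduction of about 50% (1.2.1.2.1); 10 mg BID as 5 mg tablets (6.1.1); platelet-based starts of 5, 15 and 20 mg BID for 50 to <100, 100-200 and >200 x 10^9/L (Table 6-1); entry from 75 x 10^9/L (5.2).

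**Assumptions.** Cockcroft-Gault: clearance = (140 − age) × kg × (0.85 if female) / (72 × creatinine). Ages and weights are illustrative.

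**Example.** Woman, 65 years, 60 kg, creatinine 1.8: 75 × 60 × 0.85 / (72 × 1.8) = 3825 / 129.6 = 29.5 mL/min. At creatinine 2.0, also allowed: 3825 / 144 = 26.6 mL/min.

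**Creatinine at which clearance equals 30 mL/min** = (140 − age) × kg × (0.85 if female) / 2160. An entry below 2.0 means that an eligible patient can be below 30 mL/min.

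| | 50 kg | 60 kg | 70 kg | 80 kg |
|---|---|---|---|---|
| Woman, 65 y | 1.48 | 1.77 | 2.07 | 2.36 |
| Woman, 75 y | 1.28 | 1.53 | 1.79 | 2.05 |
| Man, 65 y | 1.74 | 2.08 | 2.43 | 2.78 |
| Man, 75 y | 1.50 | 1.81 | 2.11 | 2.41 |

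**Weight below which clearance is under 30 mL/min at creatinine 2.0** = 4320 / [(140 − age) × (0.85 if female)]. At 65 years: 57.6 kg for men and 67.8 kg for women. At 75 years: 66.5 kg and 78.2 kg.

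**Dependence on the formula.** A different estimate (CKD-EPI 2021 eGFR, also an assumption, and normalised to body surface) gives at creatinine 2.0 27.2 and 25.6 for women of 65 and 75, and 36.4 and 34.2 for men. The gap persists for women but not for men.

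**Starting dose against the halved dose.**
- Platelets >200: 20 / 2 = 10 mg BID, so no excess.
- Platelets 100-200: 15 / 2 = 7.5 mg BID; 10 / 7.5 = 1.33.
- Platelets 75 to <100: taking the 10 mg start that section 2.3 justifies as the base, 10 / 2 = 5 mg BID, a factor of two. From Table 6-1 it would be 5 / 2 = 2.5 mg BID, a factor of four, but part of that comes from the trial's deliberate dose choice and not from renal function.

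**Dose taken by Day 28.** 10 × 2 × 28 = 560 mg, against 7.5 × 2 × 28 = 420 mg or 5 × 2 × 28 = 280 mg.

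**Number affected.** Not in the documents. If 0.5% to 3% of 320 patients were in the gap (assumed), that is 1.6 to 9.6 patients, of whom 0.8 to 4.8 would be on ruxolitinib. Those with platelets above 200 would have no dose excess.

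**The case against.** The best defence is that 10 mg BID is already a reduced dose, chosen partly for tolerability, and that section 2.3 reports it as well tolerated at platelets of 75,000 to 100,000/µL. This fully answers the point above 200 x 10^9/L. At 100-200 it leaves a gap of 2.5 mg per dose against an approximate recommendation. It does not settle the lower strata, because the dose rationale in section 2.3 does not discuss renal function.

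The CYP3A4 comparison is imperfect. Strong inhibitors at screening are already excluded by criterion 12, and section 6.4.2 covers inhibitors needed later, which no entry criterion could handle. Renal function is likewise handled at entry, so the difficulty lies in the marker chosen.

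There are other safeguards: criterion 11, the investigator's duty to stop harmful treatment, creatinine at scheduled visits and the DMC. They are real, but none sets a renal threshold or a starting dose.

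The formula, the weights and the frequency are assumptions, and the lead example lies only 0.5 mL/min below the line. A patient with an excess dose must combine age or low weight with raised creatinine, platelets of 200 or less and allocation to ruxolitinib. That makes the group small but does not remove it.

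Finally, section 1.2.1.2.1 advises a lower dose, not exclusion, and the SAP records that the trial stopped over recruitment. The cost in eligibility is therefore genuine, though slight.

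**Conclusion.** The concern holds. Criterion 4 does not deliver the exclusion it announces, because its measure differs from the one the protocol uses to define severe renal impairment, and no dosing rule makes up the difference. Under Cockcroft-Gault the gap reaches ordinary body sizes: women of 65 at 60 kg, women of 75 at 70 kg and men of 75 at 60 kg. The excess in starting dose ranges from none (platelets >200) through one third (100-200) to a factor of two (75 to <100, on the 10 mg base).

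The size of the gap rests on the assumed formula, ages and weights, and the number of patients cannot be derived from the documents. Sample size, events, power and the primary analysis are unaffected. This is a worthwhile low-cost correction and not a flaw in the statistical design. As the SAP reports premature termination, it now bears on the protocol as written and on any reuse of these criteria.

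**What to change.** Add to criterion 4, beside the existing creatinine limit: or calculated creatinine clearance <30 mL/min (Cockcroft-Gault, screening body weight). Adding the limit, and not substituting it, avoids newly admitting patients above 2 mg/dL.

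Section 7.1.2.1 says "The eligibility check will be embedded in the IRT system", so the calculation can be placed there. Creatinine, age, sex and weight are all collected at screening. The protocol does not say that the IRT receives these four items, so that needs confirming; otherwise the site can calculate the value and enter it.

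Exclusion is simpler than a renal dose rule, because 7.5 mg BID cannot be given as whole 5 mg tablets.

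The cost is one line of text and one calculated field, with no new test or visit. A few older, lighter patients would become ineligible.
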